11.5 Please provide a justification for your sample size

Sample Size Estimation/Power Analysis:

The required sample size is 80, 40 subjects will receive the standard treatment and 40 the experimental intervention. It was calculated by using a priori analysis to provide a power of 80%, false positive rate of 5%, 10% margin of error, and 10% calculated drop-out rate.

11.6 Data Analysis Plan: Complete description: Background, Objectives, Design, Step by Step how the project is going to be done, Data analysis plan:

Statistical Analysis: All dichotomous or categorical variables will be presented initially as counts with percentages. Any analysis looking at two dichotomous or categorical variables will be compared using Chi-Square test. Continuous outcome variables will be initially assessed for normality by the Shapiro-Wilks test and then presented as means with standard deviations if normally distributed; independent t-test will be used to determine any group differences between such variables (i.e. post-surgery – pre-surgery) or an ANOVA for three or more normally distributed variables. Otherwise, non-normally distributed outcomes will be presented as median and interquartile range (IQR) and analyzed using Wilcoxon Sign-Ranked Test or Mann-Whitney U Test for three or more variables. To test the relationship between QoL, sleep quality, healing outcomes, and intervention use, adjusted linear regression will be performed with guidance from a biostatistician. Significance will be set to $p < 0.05$. Any additional data collection or analyses will be determined in coordination and consultation with other investigators and biostatistician.

12.0
Participant Information
12.1 Subject Population:

Sample population: 80 non-emergency subjects (active-duty, retired, dependents, retired-dependents) at the USAF Graduate Periodontics Program, Lackland AFB, Texas. Subjects who meet the eligibility requirements listed below will be offered the opportunity to participate in the study. If the subject agrees to participate, they will complete an informed consent.

12.2 Age Range:

Check all the boxes that apply. If the age range of potential subjects (specimens, records) does not match the range(s) selected, please specify in the text box.

- ☐ 0-17
- ☒ 18-24
- ☒ 25-34
- ☒ 35-44
- ☒ 45-54
- ☒ 55-64
- ☒ 65-74
- ☒ 75+

18-99

12.3 Gender:

- ☒ Male
- ☒ Female
- ☐ Other

12.4 Special categories, check all that apply

- ☐ Minors /Children
- ☐ Students
- ☐ Employees - Civilian
- ☐ Employees - Contractor
- ☐ Resident/trainee
- ☐ Cadets /Midshipmen
- ☒ Active Duty Military Personnel
- ☐ Wounded Warriors
- ☐ Economically Disadvantaged Persons
- ☐ Educationally Disadvantaged Persons
- ☐ Physically Challenged (Physical challenges include visual and/or auditory impairment)
- ☐ Persons with Impaired Decisional Capacity
- ☐ Prisoners
- ☐ Pregnant Women, Fetuses, and Neonates
- ☐ Non-English Speakers
- ☐ International Research involving Foreign Nationals - Headquarters Review is necessary

You must also consider the requirements of DoDI 3216.02, Enclosure 3, paragraph 7.e.

12.5 Inclusion Criteria:

Order Number	Criteria
1	
 1. Age 18-99 2. Require a mucogingival periodontal surgery procedure 3. Have not taken antibiotics for one month 4. Are planned for non-emergent periodontal surgery 5. Are American Society of Anesthesiologists (ASA) Class I, II, III

12.6 Exclusion Criteria:

Order Number	Criteria
1	
 1. <18 years old, > 100 years of age 2. Currently pregnant or within 6 months postpartum 3. Female subjects who are nursing 4. Subjects who are decisionally challenged 5. ASA Class IV 6. Have undergone antibiotic therapy within one month prior to enrollment 7. Have undergone chronic therapy within one month prior to enrollment with medications that could affect periodontal status or healing. 8. Incompatible mobile device

13.0

Recruitment and Consent

13.1 Please describe the recruitment process, including how subjects will be identified and selected for the study.

Subjects will be screened based upon the inclusion and exclusion criteria as they present for evaluation for periodontal surgery. The daily appointment schedule will be reviewed to determine possible research candidates. Potential candidates will be either approached by the research team or will be verbally referred to the research team by the treating doctor. The study will then be explained to the potential subject in a safe and private location by a member of the research team. Subjects who meet the inclusion criteria will be approached by the PI or AIs and asked if they wish to participate in the study. Following explanation of the study and providing the subject a reasonable amount of time to make an informed decision, the informed consent for the study will be completed and the subject scheduled for surgery. A subject's verbal or written authorization must precede any physician referrals to the research team for possible recruitment and study participation.

13.2 Compensation for Participation:

Subjects will not be paid for participation in this study

13.3 Please describe the pre-screening process. If no pre-screening, enter Not Applicable in the text editor

Subjects referred to the Air Force Post-Graduate Dental School Clinic for periodontal surgery that meet the inclusion criteria and do not meet any exclusion criteria for this protocol will be approached by the PI or AIs for potential enrollment during their pre-surgical evaluation. The daily appointment schedule will be reviewed to determine possible research candidates. Potential candidates will be either approached by the research team or will be verbally referred to the research team by the treating doctor. The study will then be explained to the potential subject in a safe and private location by a member of the research team. A subject's verbal or written authorization must precede any physician referrals to the research team for possible recruitment and study participation. The study will then be explained to the potential subject in a safe and private location and smartphone compatibility will be determined for each subject.

13.4 Consent Process: Revised Common Rule, Section 219.116: General requirements for informed consent, whether written or oral, are set forth in this paragraph and apply to consent obtained in accordance with the requirements set forth in paragraphs (b) through (d) of this section. Broad consent may be obtained in lieu of informed consent obtained in accordance with paragraphs (b) and (c) of this section only with respect to the storage, maintenance, and secondary research uses of identifiable private information and identifiable biospecimens.

Are you requesting a waiver or alteration of informed consent?

☐ Yes ☒ No

Please explain the consent process:

A copy of the informed consent document will be given to the patient. During the pre-op appointment, the PI will review the terms of service for the application. Benefits, risks, and complications of participation in the study will be explained to the patient so that they best understand their proposed role in the research and what to expect. After the patient has read and understood the informed consent document, he/she will be given the opportunity to discuss the opportunity to participate in the study with friends and/or family. The PI or AIs will be available to answer any questions regarding the study. The patient will then accept or decline participation in the study. If they accept, the patient will sign the informed consent form and research-related HIPAA Authorization Document. The consenting investigator will sign the informed consent form and will attest that the informed consent process was followed, the patient understood the information contained in the informed consent, and that the patient voluntarily gave their consent for participation in the study. The subject will receive a copy of the signed informed consent document and the HIPAA Authorization Document and a second copy of

each will be placed in the research record of the subject. The consenting investigator will document the informed consent process in the research record as well as the dental record of the patient.

13.5 DoDI 3216.02 requires an ombudsman to be present during recruitment briefings when research involves greater than minimal risk and recruitment of Service members occurs in a group setting. If applicable, you may nominate an individual to serve as the ombudsman.

- ☒ N/A
☐ Propose ombudsman

13.6 Withdrawal from Study Participation:

Explain the process for withdrawal and specify whether or not the subjects will be given the opportunity to withdraw their data their data/specimens in the event they wish to withdraw from the study

At any time during the study, the subject can request to be withdrawn and have their data withdrawn. If they chose to withdraw, their surgical procedure will be continued as planned without participating in the study and subjects can remove their data from the device application.

**14.0
Risks and Benefits**

**14.1
Risks of Harm:**

Identify all research-related risks of harm to which the subject will be exposed for each research procedure or intervention as a result of participation in this study. Consider the risks of breach of confidentiality, psychological, legal, social, and economic risks as well as physical risks. Do not describe risks from standard care procedures; only describe risks from procedures done for research purposes

Potential risks associated with mucogingival surgery are that some subjects could experience bleeding, bruising, and possible infection. There is a risk of graft failure and palatal tissue necrosis. Additionally, there is a risk that the L-PRF will not reduce the subject's pain. There is a risk for potential pain, discomfort, bruising, and swelling at the site of the blood draw. Additionally, there is a risk for breach in confidentiality, since identifiable PII will be obtained for each subject. The SleepImage ring may disrupt sleep due to the vexation caused by the new wearable device.

**14.2
Measures to Minimize Risks of Harm (Precautions, safeguards):**

For each research procedure or intervention, describe all measures to minimize and/or eliminate risk of harms to subjects and study personnel

The patient will be monitored for approximately 15-30 minutes following surgery. The operating resident and periodontics faculty are readily available and well-trained in the treatment of medical emergencies related to periodontal surgery. The mucogingival surgery and L-PRF blood draw will be completed by a credentialed provider and/or periodontal resident. Any injury or adverse effects, appropriate clinical care will be given or the subject will be referred to the appropriate provider.

**14.3
Confidentiality Protections (for research records, data and/or specimens):**

Describe in detail the plan to maintain confidentiality of the research data, specimens, and records throughout the study and at its conclusion (e.g., destruction, long term storage, or banking). Explain the plan for securing the data (e.g., use of passwords, encryption, secure servers, firewalls, and other appropriate methods). If data will be shared electronically with other team members/collaborators outside the institution, describe the method of transmission and safeguards to maintain confidentiality. Explain whether this study may collect information that State or Federal law requires to be reported to other officials or ethically requires action, e.g., child or spouse abuse

The randomized subject log (Master Key of identifiable PII) will be kept separately from a confidential password-protected research spreadsheet located and stored on a government computer that will only be accessible by the PI or AIs utilizing their Common Access Card (CAC). The research spreadsheet will contain the subject's unique randomized study ID number. Additional information contained within this research spreadsheet may include the type of periodontal surgery, the diagnosis and level of difficulty of the periodontal surgery, and the length of the procedure to be used in a statistical analysis. Subsequently, the subject will be coded, using only their study number throughout the procedure and analysis. The government computer is CAC and PIN protected and contains system firewall protection. There is no intention of linking with external databases or systems nor will transmission of subject information and data for collaborative use anticipated. Subject materials that do not contain subject identification will be maintained in a locked cabinet in a locked room. A copy of the study procedure (periodontal surgery performed) specific to the subject will be placed in the subject's dental record. During the sleep data collection period, the application will store the subject's sleep parameters as previously discussed. Once the study is complete, the subject information and data will not be utilized for further research or analysis beyond the protocol stipulations unless additional IRB approval is received. This document will be the only location identifying the subject with their study number. Data from the SleepImage Ring application will be tracked using an unidentifiable number generated by the app. Subject's personal email will be used as the account username and their password will be shared with the PIs and recorded in the Master Key in the case of lost passwords. SleepImage maintains the intellectual properties of subjects' sleep data, however all data will be managed according to SleepImage's privacy policy (<http://sleepimage.com/privacy-policy/>). In their privacy policy, SleepImage states that all subjects have the right to object and erasure, the policy states that subjects have the right to "stop processing and delete personally identifiable data."

14.4 Potential Benefits:

Describe any real and potential benefits of the research to the subject and any potential benefits to a specific community or society

If the individuals in the research are considered experimental subjects (per 10 USC 980), and they cannot provide their own consent, the protocol must describe the intent to directly benefit all subjects

There are no direct benefits to the patients for participating in this study. However, patients may benefit from reduction of post-operative pain and reduction of post-operative consumption of pain medications. The use of L-PRF may also potentially enhance the healing process and improve surgical outcomes for future subjects.

14.5 Privacy for Subjects:

Describe the measures to protect subject's privacy during recruitment, the consent process, and all research activities, etc.

The study will be explained to the potential subject in a safe and private location. The subject will be given a copy of the informed consent document and HIPAA authorization document to review

on their own time at home. Throughout all clinic visits and research procedures, the subject will be in a private dental treatment room. All study related materials will be kept in a private office, on a private computer that is Common Access Card (CAC) accessible only. Additionally, the Master Key of identifiable PII and the research spreadsheet containing data will be password protected and kept totally separate from each other, both physically and electronically. As stated above, PII is stored by SleepImage, for as long as they deem necessary. However, subjects have individual rights to object and erasure of all personally identifiable data.

14.6

Incidental or Unexpected Findings:

Describe the plan to address incidental findings and unexpected findings about individuals from screening to the end of the subject's participation in the research. In cases where the subject could possibly benefit medically or otherwise from the information, state whether or not the results of screening, research participation, research tests, etc., will be shared with subjects or their primary care provider. State whether the researcher is obligated or mandated to report results to appropriate military or civilian authorities and explain the potential impact on the subject

Throughout the duration of the study, any incidental findings will be discussed with the patient just as they would during any routine dental visit. Depending on if the incidental finding is within the same surgical area of study involvement, then the discussion would be made whether or not to have the patient proceed in the study or withdrawal the patient from the study. If it is a finding that is warranted to consult with the patient's primary care provider, that would be addressed at that time.

15.0

Study Monitoring

15.1 Your study requires either Data and Safety Monitoring Plan (DSMP) or a Data and Safety Monitoring Board (DSMB).

- ☐ DSMP
- ☐ DSMB
- ☐ Both
- ☒ Not Applicable

16.0

Reportable Events

16.1 Reportable Events: Consult with the research office at your institution to ensure requirements are met. Describe plans for reporting unexpected adverse events and unanticipated problems. Address how unexpected adverse events will be identified, who will report, how often adverse events and unanticipated problems will be reviewed to determine if any changes to the protocol or consent form are needed and the scale that will be used to grade the severity of the adverse event.

Consult with the research office at your institution to ensure requirements are met

- Describe plans for reporting expected adverse events. Identify what the expected adverse events will be for this study, describe the likelihood (frequency, severity, reversibility, short-term management and any long-term implications of each expected event)
- Describe plans for reporting unexpected adverse events and unanticipated problems. Address how unexpected adverse events will be identified, who will report, how often adverse events and unanticipated problems will be reviewed to determine if any changes to the research protocol or consent form are needed and the scale that will be used to grade the severity of the adverse event

Subjects will be monitored preoperatively, perioperatively and postoperatively in the Air Force Post-Graduate Dental School. The subject will be monitored for approximately 15-30 minutes following mucogingival surgery. The subject will be monitored and appropriate emergency medical treatment will be delivered by the resident, or faculty in the event of any adverse reactions.

The operating resident and periodontics faculty are readily available and well-trained in the treatment of medical emergencies related to periodontal surgery. The mucogingival surgery and L-PRF blood draw will be completed by any current Air Force periodontal resident or staff member. Post-operative healing assessment will be completed by principle investigators only. If at any time a subject experiences any injury or adverse effects, appropriate clinical care will be given or the subject will be referred to the appropriate provider.

All events requiring prompt reporting will be sent within three (3) business days of the research team's knowledge of the event by [contact]) or by e-mail ([contact]) to the office of the San Antonio Institutional Review Board. A complete written report will follow the initial notification within ten (10) business days.

17.0

Equipment/non-FDA Regulated Devices

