Pre-Op Appointment: After informed consent is obtained at the pre-op appointment, subjects undergoing mucogingival surgery will be given a sleep monitoring device (SleepImage® Ring 2019, SleepImage, Denver, CO) and will complete a baseline QoL survey (Qualtrics Survey, 2002, Qualtrics, Seattle WA).[11, 23-26] The sleep monitoring app will be downloaded on the subjects' phone and each subject will be trained on the function of the application by the principal investigators. Principle investigators (PI) will assist subjects to download the app and establish an account during the pre-op appointment. Subjects will create an account using their personal email, date of birth, and first/last name which will generate an unidentifiable subject number, which will be tracked in a secured file (Master Key of identifiable PII) accessible only by the PIs. The subject will accrue no fees upon creation of the account. Subjects will be instructed to contact the PIs with any malfunction or questions regarding the use of the application. The application will record sleep quality index (SQI), sleep efficiency, fragmentation, latency, duration, sleep opportunity and periodicity. This specific study will only utilize the SQI as the primary outcome variable. Subjects will be instructed to wear the device nightly throughout the study. The subject will be instructed to complete the same QoL questionnaire at 24 hours, 72 hours, as well as at the one week and two week post-operative appointments (study will last a total of three weeks).

Surgical appointment:

Blood (40 mL) will be collected at the beginning of the surgical appointment and spun using a horizontal centrifuge for the group receiving L-PRF (Horizon 6, horizontal PRF centrifuge machine, 2022, Drucker Diagnostics, Port Matilda, PA). L-PRF (test group selected via computerized randomization scheme with allocation 1:1 ratio) will be made from the blood collected as per manufacturer's protocol (4 vials of blood, centrifuged at 700g for 16 minutes at room temperature). Though some providers choose to use PRF routinely in mucogingival periodontal surgeries, for this study it will be for research purposes. Subjects not receiving L-PRF will have mucogingival surgery initiated without a prior blood draw.

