The periodontal surgery will be completed by preparing the recipient site as per standard of care. The tissue harvested from the roof of the mouth will be harvested by removing the upper layer of epithelium and connective tissue technique. This technique requires secondary healing to occur and is usually the area of most pain for subjects. [20, 21] The L-PRF will be placed on donor site (for research purposes) in the experimental group and secured with palatal stent for hemostasis (for research purposes) which will remain in place for 48 hours immediately after surgery. The control group will receive an available clotting material such as Helitape®, Helicote®, or Surgicel®, which is the standard of care, placed on the donor site and secured with a palatal stent for hemostasis with identical post-operative wearing instructions as the experimental group. All subjects will receive post-operative ibuprofen and acetaminophen for pain management. Time and amount of medication will be annotated and recorded at post-operative appointments.

Post-Op Appointments:

At the follow-up appointments, subjects will complete the one- and two-week questionnaires to evaluate their perceived QoL since the time of the surgical intervention (see questionnaire). The healing of the palatal harvest site will be evaluated by two calibrated clinicians using the Landry et al. healing index on a scale of 1-5 (see data collection sheet).[18] The provider will complete a routine post-operative examination which includes visualizing and palpation of surgical area for swelling, removal of sutures, evaluation of pain, noting any purulence upon palpation, noting any tenderness upon palpation of lymph nodes, and temperature obtained to indicate yes/no for infection. This data collection is considered standard of care. At the final follow-up appointment subjects will return the SleepImage ring to the primary investigators. If the sleep monitoring device is lost or damaged prior to the end of the trial, the study will cover the cost of replacement.

10.2 Data Collection:

Describe all the data variables, information to be collected, the source of the data, and how the data will be operationally measured.

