After informed consent is obtained at the pre-op appointment, subjects undergoing mucogingival surgery will be given a sleep monitoring device (SleepImage® Ring 2019, SleepImage, Denver, CO) and will complete a baseline QoL (Qualtrics XM®, 2002, Qualtrics, Seattle WA) [11, 23-26] The sleep monitoring app will be downloaded on subjects' phones and each subject will be briefed on the function of the application. Subjects will be instructed to wear the device nightly throughout the study. The subject will be instructed to complete the same QoL questionnaire at 24 hours, and 72 hours, as well as at the one-week and two-week post-operative appointments. The subjects' medical history will be coded and the following conditions will be noted: L-PRF, no-PRF, type of surgery, type of sedation, experience level of clinician, length of surgery, size of harvest, smoking, diabetes. Subjects' age and sex will also be documented. All of these parameters are reflected in the total data collection sheet. The mucogingival surgery will have been recommended and accepted by subjects as the standard of care.

At the follow-up appointments, subjects will complete the one- and two-week questionnaires to evaluate their perceived QoL since the time of the surgical intervention (see questionnaire). The healing of the palatal harvest site will be evaluated by two calibrated clinicians using the Landry et al. healing index on a scale of 1-5 (see data collection sheet).[18] The provider will complete a routine post-operative examination which includes visualizing and palpation of the surgical area for swelling, removal of sutures, evaluation of pain, noting any purulence upon palpation, noting any tenderness upon palpation of lymph nodes, and temperature obtained to indicate yes/no for infection. This data collection is considered standard of care. Data from the QoL surveys will be analyzed using Qualtrics® data system. Sleep data will be extracted and analyzed in the SleepImage® portal.

10.3 At any point in the study, will you request, use, or access health information in any form, including verbal, hard copy and electronic?

☒ Yes ☐ No

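### Healing is graded by the principal investigators with no masking and no separation of operator from grader, so the judged 1–5 healing index is open to detection bias.

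*Combined protocol and SAP*

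**What the plan says.** On who grades, section 16.1 (Reportable Events) states: "Post-operative healing assessment will be completed by principle investigators only". Sections 10.1 (Study Procedures) and 10.2 (Data Collection) both state: "The healing of the palatal harvest site will be evaluated by two calibrated clinicians", using a 1–5 index at the one- and two-week visits. Neither identifies the two clinicians.

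On access to arm information:
- Section 10.1 says the app-generated subject number is "tracked in a secured file (Master Key of identifiable PII) accessible only by the PIs".
- Section 14.3 gives that file a second name: "The randomized subject log (Master Key of identifiable PII) will be kept separately from a confidential password-protected research spreadsheet". The spreadsheet is open to the PI and the additional investigators.
- Section 10.2 makes the arm a recorded variable: "the following conditions will be noted: L-PRF, no-PRF". It places this on the total data collection sheet. The healing score is also referred to a data collection sheet.

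On who operates, section 16.1 allows any current periodontal resident or staff member. It does not exclude the principal investigators.

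On masking, the plan is silent. It does not mask graders, subjects or analysts, does not declare the study open-label, and has no rule separating operator from grader.

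**The concern.** The healing index is a clinician's judgement. A grader who knows the arm and expects a benefit can score the treated site slightly higher without meaning to. Section 14.4 shows that such an expectation exists, since it says L-PRF may enhance healing. Randomization does not protect against this, because the bias arises when the outcome is assessed. Calibration improves agreement between graders but does not conceal the arm.

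Healing status at one and two weeks is an objective under both specific aims (section 9.3). It is also one of the terms in the planned adjusted regression of QoL, sleep quality, healing and intervention (sections 11.1 and 11.6). A grading bias would affect both.

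This is also a place where protection is still feasible. Only the L-PRF arm has blood drawn (section 10.1), so subjects can infer their arm and self-reported QoL is hard to mask. For healing, both arms wear a palatal stent with the same instructions for 48 hours, the first grading is at one week, and people other than the graders may operate.

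**Working it through.** **Reading the sections together**

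1. Sections 10.1 and 10.2 require two calibrated clinicians. Section 16.1 requires principal investigators, in the plural. Two calibrated principal investigators would satisfy all three sections. The descriptions differ and should be aligned, but they are compatible.
2. The principal investigators have the Master Key, which section 14.3 calls the randomized subject log, and they can open the research spreadsheet. The arm is noted on the total data collection sheet. No section says who generates or keeps the allocation list.
3. No rule prevents a grader from having operated on the subject or from seeing the arm before grading.

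**Size, as an illustration**

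The plan has no figure to reproduce here: it gives no SD for the healing index, no expected distribution and no estimate of rater bias.

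Inputs:
- 40 per arm and 10% dropout (section 11.2), so 40 × 0.90 = 36 graded per arm.
- A 5% significance level (section 11.1). Sidedness is not stated; two-sided is assumed.
- Assumed SD of the index: 0.8, range 0.7–1.0.
- Assumed fraction f of L-PRF grades raised by one point: 1/10 or 1/4. No true effect.

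Simple version: standardized shift = f / SD; noncentrality = shift × √(36/2) = shift × 4.243; false-positive rate from the noncentral t with 70 degrees of freedom and critical value 1.994. For f = 1/4 and SD 0.8, the shift is 0.25/0.8 = 0.31, the noncentrality is 1.33 and the rate is 26%.

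Random one-point upgrades also add variance f(1 − f) in the L-PRF arm. The pooled SD becomes √(SD² + f(1 − f)/2). For f = 1/4 and SD 0.8 this is √(0.64 + 0.094) = 0.857, the noncentrality is (0.25/0.857) × 4.243 = 1.24 and the rate is 23%.

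| f | SD | Simple rate | Pooled SD | Noncentrality | Rate with added variance |
|---|---|---|---|---|---|
| 1/10 | 0.7 | 9.2% | 0.731 | 0.58 | 8.8% |
| 1/10 | 0.8 | 8.2% | 0.828 | 0.51 | 8.0% |
| 1/10 | 1.0 | 7.0% | 1.022 | 0.42 | 6.9% |
| 1/4 | 0.7 | 32.1% | 0.764 | 1.39 | 27.8% |
| 1/4 | 0.8 | 25.8% | 0.857 | 1.24 | 23.1% |
| 1/4 | 1.0 | 18.2% | 1.046 | 1.01 | 17.0% |

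The scale also stops at 5, so a grade of 5 cannot be raised. Simulating normal scores with SD 0.8, rounded and limited to 1–5, 36 per arm and f = 1/4, the t-test rejects in about 21%, 16% and 14% of trials for latent means of 3, 4 and 4.3. Mann-Whitney gives 20%, 17% and 15%.

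For f = 1/4 the range is therefore roughly 14–28%: the lower end is SD 0.8 with a strong ceiling, the upper end SD 0.7 with no ceiling. Combining SD 1.0 with a mean of 4.3 lowers it a little further, to about 12%. For f = 1/10 the rate is about 7–9% before the ceiling and 6–8% with it.

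**The case against.** Four points can be made for the plan, and each limits how far the concern reaches.

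First, a reader might infer that section 16.1 contradicts section 10.1 by naming different graders. The documents do not show this, because the two unnamed clinicians may be the principal investigators. Only the need for consistent naming stands.

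Second, a reader might infer that the graders hold the treatment codes. That goes beyond the text. The Master Key is described as linking identity to study number and as holding app passwords. The spreadsheet contents listed in sections 10.14 and 14.3 do not include the arm, and the total data collection sheet is not said to be that spreadsheet. The name of the log and the recording of the arm make access plausible. What is established is that nothing prevents graders from knowing the arm.

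Third, a reader might infer that the main result is compromised. Section 10.1 names SQI as the primary outcome variable. It is recorded by the ring, so a grader's knowledge of the arm does not reach it directly. Healing is a supporting objective and one regression term.

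Fourth, the size is hypothetical. This is correct. The SD and the upgrade fractions are assumptions, and the simple 26% overstates its own scenario by ignoring the added variance and the ceiling. The calculation also assumes that the upgrade passes fully into whatever score is analysed, although two people grade. The direction of the effect does not depend on these choices.

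None of this supplies the missing safeguard.

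**Conclusion.** The concern holds in limited form. If the plan is followed as written, a subjective 1–5 score is graded by investigators whom nothing keeps from knowing the arm and who may themselves have operated. The healing objectives under both aims, and the healing term in the regression, are open to detection bias; the SQI is not directly affected. The documents support neither a proven conflict over who grades nor a statement that the graders keep the allocation.

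Confidence is high that masking and operator–grader separation are absent from the plan. The size of any bias cannot be known from the documents. Under the stated assumptions the nominal 5% error for healing becomes about 7–9% with slight bias (one grade in ten) and roughly 14–28% with marked bias (one in four). These figures are illustrative and are not estimates for this trial. The change should be made because it is inexpensive.

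**What to change.** 1. Identify the graders in the same terms in sections 10.1, 10.2 and 16.1.
2. State that neither grader operated on that subject, and that neither can see the arm until both the one-week and two-week gradings are locked. This covers the allocation list, the arm column and the sheet used for grading.
3. Have an existing investigator who does not grade hold the arm data in a separate file, and say who generates and keeps the allocation list.
4. Ask subjects not to mention the blood draw at grading visits.
5. Do not let the grader be the provider who does the routine post-operative examination if that would reveal the arm.
6. If masking is not practicable for some subjects, say so and report healing as an unmasked outcome.

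The cost is protocol wording, file permissions and some rota planning. Staffing details are not in the supplied text, so whether enough non-operating graders are available has to be confirmed locally. The documents also do not say whether remnants of either donor-site material can be seen at one week; if they can, masking at that visit would be incomplete and item 6 applies.
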